- 9) Other concomitant drugs: drug name, reason for use, administration route, dose, and administration period
- 10) Drugs/combination therapies other than medication for ulcerative colitis

Presence or absence of drugs/combination therapies other than medication for ulcerative colitis, name of therapy, and therapeutic duration

11) Presence or absence of onset of tuberculosis or serious respiratory disorders

Examination day, imaging diagnostic method, abnormal findings, and abnormality

12) Mayo Score

Examination day (at initiation of administration, week 4, 8, 16, 24, 32, and 52 of administration, and discontinuation of administration)

13) CRP

Examination day (at initiation of administration, week 4, 8, 16, 24, 32, and 52 of administration, and discontinuation of administration)

14) Endoscopic finding

Examination day (at initiation of administration, week 24, 52 of administration, and discontinuation of administration)

15) Overall improvement (judgment by attending physician)

Judgment day (at week 52 of administration or at discontinuation)

Overall improvement (Remarkably effective, Effective, Ineffective, and Unevaluable)

16) Adverse events (including abnormal change in laboratory values)

Occurrence of adverse events, name of adverse events, onset day, seriousness, causal relationship to this drug, suspected drug(s), symptom and clinical course, treatment (with this drug or symptomatic treatment), outcome, laboratory values (if abnormally changed), and judgment reason if no causality

17) Key survey items

Infection, tuberculosis, malignant tumor, administration site reaction, autoimmune disease, pancytopenia, demyelinating disorders, congestive cardiac failure, and interstitial pneumonia

18) Measurement of anti-adalimumab antibody

If measurement of anti-adalimumab antibody is judged to be necessary

9. Analysis and Methods

- (1) Analytical items
 - 1) Patient population
 - 1. No. of enrolled patients
 - 2. No. of CRFs recovered
 - 3. Safety evaluation set
 - 4. Efficacy evaluation set
 - 2) Safety
 - 1. List of adverse reactions and infections
 - 2. Factors likely to affect the safety

- Incidence of adverse reactions by patient background
- Presence or absence of the use experience with anti-TNFα preparation and the relationship of safety.
- Safety in Long-Term administration
- Relationship of safety when anti-adalimumab antibody was determined
- Safety in patients conducting self-administration

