12.4. Assessment period for partial Mayo score

Time allowance of assessment period with the first administration date of Humira as 1 is as follows:

Assessment period	Time Allowance(Day)
At the first administration	-14 ~ 1 (scheduled date: 1)
Week 4 of administration	15 to 42 (scheduled date: 29)
Week 8 of administration	43 to 70 (scheduled date: 57)
Week 16 of administration	98 to 126 (scheduled date: 112)
Week 24 of administration	155 ~ 183 (scheduled date: 169)
Week 52 of administration	337 ~ 393 (scheduled date: 365)
At discontinuation	The final administration date of Humira + 14 (scheduled date:
	the final administration date of Humira)
At final assessment	Data for the final assessment period among the assessment
	applicable to the Time Allowance of each assessment period.

The data for analysis should derive from the one the closest to the scheduled date within Time Allowance. If there are more than one data dated on the same day, select the higher value.

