12.6. Assessment period for CRP

Time allowance of assessment period with the first administration date of Humira as 1 is as follows:

Assessment period	Time Allowance(Day)
At the first administration	-14 ~ 1 (scheduled date: 1)
Week 4 of administration	15 to 42 (scheduled date: 29)
Week 8 of administration	43 to 70 (scheduled date: 57)
Week 24 of administration	155 ~ 183 (scheduled date: 169)
Week 52 of administration	337 ~ 393 (scheduled date: 365)
At discontinuation	The final administration date of Humira + 14 (scheduled date:
	the final administration date of Humira)
At final assessment	Data for the final assessment period among the assessment
At final assessment	applicable to the Time Allowance of each assessment period.

The data for analysis should derive from the one the closest to the scheduled date within Time Allowance. If there are more than one data dated on the same day, select the higher value.

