Note: the patient background factors are as follows:

Age (year), the elderly, pediatrics, sex, body weight (kg), BMI (kg/m²), duration of illness (year), complications, complication: hepatic function disorder, complication; renal impairment, complication: blood disorder, complication: respiratory disorder, complication: diabetes mellitus, complication: osteoporosis, complication: malignant tumour, medical history; medical history: tuberculosis, medical history: non-tuberculous mycobacteriosis, medical history: interstitial pneumonia, medical history: bronchitis bacterial, medical history: aplastic anaemia, medical history: pancytopenia, medical history: malignant tumour, allergy history, smoking history, detailed history of smoking history, the administration status of Humira: self-administration, prior medication, prior medication: biological product, prior medication Infliximab, prior medication: other biological product, prior medication: aminosalicylic acid drug, prior medication: corticosteroids, prior medication: azathioprine, prior medication 6-mercaptopurine, prior medication: azathioprine & 6-mercaptopurine, prior medication: tacrolimus & ciclosporin, prior treatment, prior treatment: leukocytapheresis, prior treatment: surgery, prior treatment: enteral nutrition therapy, prior treatment: intravenous nutrition therapy, concomitant medication, concomitant medication: aminosalicylic acid drug, concomitant medication: corticosteroids, concomitant medication: azathioprine, concomitant medication: 6-mercaptopurine, concomitant medication: azathioprine & 6-mercaptopurine, concomitant medication: tacrolimus & ciclosporin, concomitant treatment, concomitant treatment: leukocytapheresis, concomitant treatment: surgery, concomitant treatment: intravenous nutrition therapy, concomitant treatment: enteral nutrition therapy, site of disease by type, partial Mayo score, CRP

"3.4.1 Aggregation for effectiveness per patient background factor (partial Mayo score)" Patients for analysis: patients in the effectiveness analysis group

Analysis objective: to show the remission of partial Mayo score at the final assessment as the primary endpoint per patient background factor and analyze them.

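### Week 32 partial Mayo and Week 16 and 32 CRP are scheduled in the protocol but have no window in the SAP, so the final-assessment endpoint can revert to Week 24 or earlier although a later score is on the CRF

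*Protocol*

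**What the plan says.** Protocol section 8(3) gives one schedule for item 12 (Mayo score) and item 13 (CRP): "Examination day (at initiation of administration, week 4, 8, 16, 24, 32, and 52 of administration, and discontinuation of administration". Endoscopy (item 14) is sparser: "Examination day (at initiation of administration, week 24, 52 of administration, and discontinuation of administration". A Week 32 score will therefore normally be a partial Mayo score.

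SAP 12.4 lists partial Mayo windows for baseline, Weeks 4, 8, 16, 24 and 52, discontinuation and final assessment. The Week 16 row is "98 to 126 (scheduled date: 112". Week 24 is "155 ~ 183 (scheduled date: 169", and the next scheduled row is Week 52, "337 ~ 393 (scheduled date: 365". SAP 12.6 (CRP) has the same rows except Week 16: after Week 8, "43 to 70 (scheduled date: 57", it goes straight to Week 24 and then to Week 52.

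Both sections analyse the value closest to the scheduled date within the window. Final assessment is defined as "Data for the final assessment period among the assessment" values that fall in one of the listed windows. The discontinuation row ends 14 days after the last administration, and its first day is not given.

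In SAP 13.3, the objective of chart 3.4.1 is "to show the remission of partial Mayo score at the final assessment as the primary endpoint" by patient background factor.

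**The concern.** Week 32 is the only scheduled visit between Weeks 24 and 52. With no row for it, the partial Mayo time course (charts 3.1.4, 3.1.5.1, 3.1.5.2 and 3.6) and the CRP summary (chart 3.5) have no scheduled point in the part of the year that says most about durability. Protocol section 9 and SAP 5.1 both list long-term efficacy, including secondary failure, as an analysis item.

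The same omission affects an endpoint. Final assessment can draw only on listed windows, so the window table decides which score enters chart 3.4.1, where remission is tested against a long list of background factors. A patient with a usable Week 32 score but nothing later in a window is classified on an older score.

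The full Mayo windows in SAP 12.3 (Weeks 24 and 52) follow the endoscopy schedule and raise no issue. That explanation does not extend to partial Mayo or CRP, which need no endoscopy.

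**Working it through.** **Planning figures.** Protocol Table 1: 1500 × 0.30 = 450 patients at Week 52; 450 × 0.70 = 315 with a Mayo score; half-width 1.96 × √(0.3 × 0.7 / 315) = 5.06%, giving 24.9 to 35.1%. This reproduces the table, and nothing below changes it.

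**Visits against windows.** With the first dose as Day 1, the nominal day is 7 × week + 1.

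| Visit | Nominal day | Partial Mayo window (12.4) | CRP window (12.6) |
|---|---|---|---|
| Week 4 | 29 | 15–42 | 15–42 |
| Week 8 | 57 | 43–70 | 43–70 |
| Week 16 | 113 | 98–126 | none |
| Week 24 | 169 | 155–183 | 155–183 |
| Week 32 | 225 | none | none |
| Week 52 | 365 | 337–393 | 337–393 |

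**Days outside every scheduled window, after Day 14.**
- Partial Mayo: Days 71–97, 127–154 and 184–336. Only the last contains a protocol visit (Week 32), and it spans 336 - 184 + 1 = 153 days.
- CRP: Days 71–154 (154 - 71 + 1 = 84 days, containing Week 16) and Days 184–336 (153 days, containing Week 32). These are two separate gaps.

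**What the discontinuation row recovers.** SAP 10.1 treats a patient as discontinued if the last administration falls before first administration + 336 days, that is, before Day 337.
- If the window runs from last dose to last dose + 14, a last dose on Days 170–336 can give a usable value within Days 184–336. A Day 225 score is kept only if the last dose was on Days 211–225.
- If it is read as in SAP 12.5, which starts at Day 1 for discontinued patients, the closest score before the last dose can qualify. A Week 32 score could then serve for someone who stopped on, say, Day 280.

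**Who falls back.**
- Patients on drug to Day 337 or later: final assessment is Week 52 if scored, and otherwise Week 24 or earlier. On the planning figures, up to 450 - 315 = 135 patients reach Week 52 unscored (135 / 1500 = 9%).
- Discontinued patients: only those without an in-window discontinuation score. For scale, assume a constant stopping rate, S(d) = (1 - D)^((d - 1)/364). The number with a last dose on Days 184–336 is 1500 × [S(184) - S(337)]: about 325 at D = 70% (the plan's figure), 268 at 50% and 175 at 30%. These are the patients for whom the discontinuation row matters most. They are not a count of fallbacks.

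**The case against.** A reader might infer that every value from Day 184 to 336 is thrown away and that a Week 32 score can never be used. The documents do not support either statement. The discontinuation row keeps values near the last dose and feeds final assessment; read like SAP 12.5, it keeps more. Fallback needs both the Week 52 value and the discontinuation value to be absent. The Week 16 CRP gap is a separate matter.

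Nor can the plan's 30% be applied to late stoppers to count lost scores. That rate is for Mayo scores not assessed among patients remaining at Week 52, borrowed from CDAI recording in a Crohn's disease survey. It is not a rate of missing partial Mayo at discontinuation.

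It is also fair to say that late failure shows elsewhere. Chart 3.4, also labelled a primary endpoint, uses general improvement with the wide window of SAP 12.5 and is unaffected. Charts 1.6.2 and 1.7 show continuation on drug and discontinuation for lack of effectiveness. CRP enters no over-time test and is only summarised in chart 3.5.

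Finally, SAP 12.7 uses Weeks 4, 8, 16, 24 and 52 for continuation, and the protocol promises change up to Week 52 rather than a table for every visit, so the set may have been chosen deliberately. But 12.7 includes Week 16, which 12.6 omits, so one common set does not explain both tables. A choice of display points also does not explain why a recorded Week 32 score should be barred from final assessment.

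These arguments limit the size of the point. The missing rows and the fallback rule remain.

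**Conclusion.** The point holds in this form. Week 32 partial Mayo and Week 16 and 32 CRP have no scheduled window and no stated reason for the omission. For patients still on treatment, in-between values are not analysed. The chart 3.4.1 endpoint reverts to Week 24 or earlier when neither a Week 52 nor a discontinuation-window score exists, even with a Week 32 score on the CRF.

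The figure of 135 is an upper planning figure. It assumes 70% dropout and 30% unassessed at Week 52, applies a Mayo-score rate to partial Mayo (which may be recorded more often), and helps only where a Week 32 score was recorded. How many patients would change remission status, and in which direction, cannot be derived from the documents; that the omission hides late loss of response is plausible but not shown. The addition from discontinued patients cannot be fixed until the discontinuation window has a first day. The sample size is unaffected. This is an inexpensive change that should be made.

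**What to change.** 1. Add a Week 32 row to SAP 12.4 and 12.6, for example Day 211–239, scheduled Day 225 (±14 days, as at Week 24).
2. Add a Week 16 row to SAP 12.6 that matches the partial Mayo row in 12.4. Either use Day 98–126, scheduled 112, as written, or move both to Day 99–127, scheduled 113, which is the Week 16 day in 12.7. One visit should not have two definitions.
3. Carry Week 32 partial Mayo into charts 3.1.4, 3.1.5.1, 3.1.5.2 and 3.6 and into the final-assessment rule. Carry Week 16 and Week 32 CRP into chart 3.5.
4. State the first day of the discontinuation window in 12.4 and 12.6.
5. Days 184–210 and 240–336 stay outside scheduled windows after step 1, so say whether final assessment may use an out-of-window last score.

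If the visits were left out on purpose, give the reason instead.

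The cost is a few SAP lines and some extra table columns; no new data are needed. One side effect is that chart 3.1.4 uses a Bonferroni adjustment. If all seven post-baseline rows are tested, adding Week 32 moves the per-test level from 0.05/7 = 0.0071 to 0.05/8 = 0.0063. If the charts have already been run, the added results can be reported as supplementary and labelled so.

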			complications", "presence of medical
			history", "presence of
			complication/others" and "presence of
			medical history/others" were amended for
			clarification
			• The definitions of "HBs antigen test",
			"HBs antibody test", "HBc antibody test",
			"HBV-DNA quantification test" and
			"Tuberculin test or IGRA test" were
			changed
			• The definitions of "Chest X ray or CT
			test", "tuberculosis test" and "Hepatitis B
			test" were added
			• "To describe the drug name" was
			added to the definitions of "presence of
			prior medication" and "presence of
			concomitant medication"
			■ 11. How to stratify data
			• "Circulatory disorders" was deleted in
			"Detailed classification of complications"
			"Gastrointestinal disorder" and
			"Collagen disorder" were deleted in
			"Other classifications of complications"
			• "Presence of decreased response",
			"acute events", "delayed events" and
			"Unknown/Not provided" were deleted in
			"Detailed classification of 'using'
			biological products"
			■ 13.1 General
			• Analysis items of 1.1, 1.3.1, 1.4 and
			1.4.1 were changed
			• 1.4.4 was added
			• Analysis target in 1.7 and 1.13 was
			changed
			Analysis target and items were

Version	Date of	Prepared/revised	
No.	preparation/revision	by	Reasons
		-	changed in 1.12.
			• Analysis target in 3.6 was changed
			and the table number was also changed to
			1.6.2
			■ 13.2 Safety
			• Analysis items of 2.4.1, 2.4.2, 2.4.3,
			2.4.4, 2.9 and 3.4 were changed
			• 2.5.1, 2.9.xx, 2.18.1 and 2.19 were
			added.
			• Remarks were added in 2.6
			Analysis target, analysis objective and
			analysis items were changed in 3.4.1.
2.0	February 6, 2018	[name]	■ General
			Names of external files were amended
			for final report
			■ 6. Presence/absence of analysis and its
			schedule
			Final report period was added
			■ 7.2. Dictionary in use
			MedDRA/J version update
			■ 8. Definitions of groups used for
			analysis
			• Exclusion items for "patients excluded
			from the efficacy analysis group" were
			added.
			■ 9.3. Digits displayed for figures
			Descriptions on CRP were added
			■ 10.1 General
			• The definition of "Administration
			status (dosage and administration)" was
			amended.
			• "Reasons for discontinuation/other
			reasons", "detailed classification of
			smoking history", "presence of prior
			medication (azathioprine &

Version	Date of	Prepared/revised	Reasons
No.	preparation/revision	by	Reasons
			6-mercaptopurine)", "presence of prior
			medication (tacrolimus & ciclosporin)",
			"presence of combination drug
			(azathioprine & 6-mercaptopurine)", and
			"presence of combination drug (tacrolimus
			& ciclosporin)" were newly added.
			• The description of "presence of
			smoking history" was amended for
			clarification.
			The conditions for drug code were
			added in "presence of prior medication"
			and "presence of presence of concomitant
			medication"
			• "Presence of prior medication
			(aminosalicylic acid drug)", "presence of
			prior medication (corticosteroids)",
			"presence of prior medication
			(azathioprine)", "presence of prior
			medication (6-mercaptopurine)", and
			"presence of prior medication
			(antibiotics)", were added for the
			conditions of the survey form.
			The condition of ciclosporin was
			added in "presence of prior medication
			(others)" and "concomitant medication
			(others)".
			■ 10.3 Effectiveness analysis
			• "Responder of partial Mayo score"
			was newly added
			Endoscopy results were added
			■ 11. How to stratify data
			• "Reasons for discontinuation/other
			reasons", "detailed classification of
			smoking history" and "disease site per
			type" were newly added.

Version	Date of	Prepared/revised	Reasons
No.	preparation/revision	by	Reasons
			Azathioprine & 6-mercaptopurine
			were added and tacrolimus was replaced
			with tacrolimus & ciclosporin in "detailed
			classification of prior medications for
			colitis ulcerative" and "detailed
			classification of concomitant medications
			for colitis ulcerative"
			• "Unknown/Not provided" was added
			in the discontinuation reason for the
			detailed classification of 'using' biological
			products".
			• "Normal or remission-phase mucosa,
			mild, moderate, severe in severity" was
			added in "endoscopy results"
			■ 12.3 Assessment period of Mayo score
			• The definitions of the time of
			discontinuation and the time of final
			assessment were added.
			■ 12.4 Assessment period of partial Mayo
			score
			Time point was added
			■ 12.6 Assessment period of CRP
			Time point was added
			■ 12.7 Assessment period for the
			continued administration of Humira
			Time point was added
			■ 13.1 General
			• Analysis items of 1.4, 1.4.1, 1.4.4 and
			1.12 were changed
			• Analysis target was changed in 1.6.2
			Aggregation details was changed in
			1.7.1
			■ 13.2 Safety
			• The period classification was changed
			in 2.1

Version No.	Date of preparation/revision	Prepared/revised by	Reasons
	proparation to vision		 Analysis items were changed in 2.9 and 2.20 13.3 Effectiveness 3.1.5.2, 3.1.7.2, 3.6 and 3.7 were newly added Analysis details was changed in 3.1.7.1 and 3.4 Analysis objective was changed in 3.5 Analysis item was changed in 3.5 Analysis target and objective were changed in 3.4.1
2.1	March 12, 2018.	[name]	■ 11. How to stratify data • "Partial Mayo score" was changed Changed from "≥6 and <9" to "≥6 and ≤9"

2. Definitions of terms and abbreviations

The terms and abbreviations used in this analysis plan are as follows:

Term and abbreviation	Definition
	Any untoward or unintended symptoms (including abnormal
Adverse event	laboratory findings), condition or illness which are not always
	related to Humira.
	Adverse events which occur from the first administration date of
Adverse events in the	Humira through Week 56 of administration (Day 1 + 392)
safety analysis period	Note that adverse events in discontinued cases should be the ones
salety analysis period	which occur from the first administration date of Humira through
	the final administration + 28 days.
	Adverse events which occur prior to the first administration date of
Adverse events not in the	Humira or beyond Week 56 of administration (Day 1 + 392).
safety analysis period	Note that adverse events in discontinued cases should be the ones
salety analysis period	which occur prior to the first administration date of Humira or
	beyond the final administration + 28 days.
Adverse reaction	Adverse events for which the causal relation with Humira cannot be
Adverse reaction	ruled out.
Adverse reactions in the	Adverse events which occurred in the safety analysis period and for
safety analysis period	which the causal relation with Humira cannot be ruled out.
Adverse reactions not in	Adverse events which occurred not in the safety analysis period and
the safety analysis period	for which the causal relation with Humira cannot be ruled out.
	It includes number of cases, mean, standard deviation, minimal
Summary statistics	value, 1st quartile value, median, 3rd quartile value and maximal
	value.
MedDRA/J	Medical Dictionary for Regulatory Activities / Japanese edition
SOC	System Organ Class in MedDRA/J
PT	Preferred Terms in MedDRA/J
LLT	Lowest Level Terms in MedDRA/J
IGRA test	Interferon gamma release assay
Partial Marya caara	Total of stool frequency sub score, rectal bleeding sub score and
Partial Mayo score	physician's global assessment
Mayo score	Total of partial Mayo score and endoscopy score
GB	Green book. Guide on re-examination

3. Objective of this statistical analysis plan

3.1. Objective of developing this statistical analysis plan

This statistical analysis plan aims at planning in advance the items regarding the statistical analysis activities which are conducted in accordance with the protocol of "Special drug-use survey for Humira[®] for subcutaneous use only (the long-term survey on colitis ulcerative)" (hereinafter referred to as "this survey"). This is a survey conducted in accordance with GPSP Ministerial Ordinance, and is a document used to prepare the regulatory report of Humira's special drug-use survey and application documents for re-examination.

4. The survey outline

4.1. Survey objective

This survey aims at exploring the following items in colitis ulcerative patients who used Humira, as the special drug-use survey of Humira [®] for subcutaneous use only (the long-term survey).

- 1) Unexpected adverse reactions (Specifically important adverse reactions)
- 2) The onset status of adverse reactions in the practical use
- 3) Factors which may affect the safety and effectiveness

<Priority survey items>

The onset status of infection, tuberculosis, malignant tumour, administration site reactions, autoimmune disease, pancytopenia, demyelinating disease, cardiac failure congestive and interstitial pneumonia

If an intestinal infection occurs, investigate the virus or bacterium causing it whenever possible.

